1. PROTOCOL SUMMARY

PROTOCOL NUMBER: RRMM-4047-PH4

PROTOCOL TITLE: A PHASE 3, MULTICENTER, RANDOMIZED, OPEN-LABEL STUDY TO COMPARE THE EFFICACY OF POMALIDOMIDE AND LOW-DOSE DEXAMETHASONE (Pom/dex) VERSUS HIGH-DOSE DEXAMETHASONE (DEX) IN SUBJECTS WITH RELAPSED AND/OR REFRACTORY MULTIPLE MYELOMA (RRMM)

1.1 Objectives

Primary: to compare progression-free survival in subjects with RRMM who are receiving Pom/dex vs subjects receiving DEX alone in a randomized multicenter setting.

Secondary: to compare the Overall Survival (OS) in subjects with RRMM who are receiving Pom/dex vs subjects receiving DEX alone in a randomized multicenter setting.

1.2 Study design

This is a Phase 3, randomized, open-label, multicenter study comparing two treatment regimens for subjects with RRMM. Eligible subjects will be randomized in a 1:1 ratio to receive either the control DEX or Pom/dex. Randomization will be stratified by β_2 microglobulin levels ($<$ vs ≥ 3 mg/L), prior lines of anti-MM treatment (3 vs >3) and subjects' age (\leq vs >75 years). The primary endpoint of this Phase 3 study is progression-free survival. Subjects will receive the treatment determined by randomization in 28-day cycles until disease progression or unacceptable toxicity (whichever occurs first).

Long-term follow-up for disease status and survival will continue until the subject has withdrawn consent for further participation, is lost to follow-up, has died, or the Sponsor makes a decision to close the study.

1.3 Trial population and sample

The trial population will comprise patients with multiple myeloma (MM) who are relapsed or refractory to the following prior therapies:

- IMiDs (Immunomodulatory drugs), e.g. lenalidomide (Revlimid®) \pm dexamethasone,
- proteasome inhibitors, e.g. bortezomib (Velcade®) \pm dexamethasone,
- \pm autologous stem cell transplantation (ASCT)

Relapse is defined as progression of disease after an initial response to previous treatment, more than six months after cessation of treatment.

Refractory is defined as resistance to treatment due to lack of response or progression of disease during treatment or within six months after cessation of treatment.

The patients must be ≥ 18 years of age.

[name], 2015

The patients must have given informed consent before any study related procedures are performed.

The patients must meet all eligibility criteria in chapter 5.

Approximately 250 subjects will be enrolled, in 20 different sites.

1.4 Study treatment

- Control Arm: **High-dose Dexamethasone** 40 mg PO or IV on Days 1-4, 9-12, 17-20.
- Interventional Arm: **Pomalidomide** 4 mg PO on Days 1–21 of a 28 days cycle **and Low-dose Dexamethasone** 40 mg (20 mg for >75 years) PO or IV on Days 1, 8, 15, 22.

1.5 Primary endpoint

Progression-free survival (PFS)

1.6 Secondary endpoint

Overall Survival (OS)

1.7 Statistical methods

The primary efficacy endpoint is PFS, defined as the number of months from randomization to the earlier of disease progression or death due to any cause. The primary analysis of PFS will include all randomized subjects (intention-to-treat population). PFS distribution times will be summarized descriptively using the Kaplan-Meier method. Median PFS will be estimated for each treatment group from the 50th percentile of the corresponding Kaplan-Meier estimates. The primary inferential comparison between treatment groups will use the log-rank test stratified by the randomization stratification factors. The hazard ratio for treatment group will be estimated using a stratified Cox proportional hazards model. A total of 125 progression events will provide 90% power to detect, with a 1-sided significance level of 0.025, a 50% increase in median PFS for the Pom/dex arm vs the DEX arm (3 vs 2 months, respectively).

The distribution of overall survival times will be summarized descriptively using the Kaplan-Meier method. Median overall survival will be estimated for each treatment group from the 50th percentile of the corresponding Kaplan-Meier estimates. The primary inferential comparison between treatment groups will use the stratified log-rank test. The hazard ratio for treatment group will be estimated using a stratified Cox proportional hazards model.

2. BACKGROUND (Disease & Treatment)

2.1 Multiple Myeloma

MM is a plasma cell disorder, characterized by uncontrolled and progressive proliferation of a plasma cell clone. In the majority of patients, the malignant plasma cells produce a monoclonal protein (M protein or paraprotein), which is an immunoglobulin (Ig) or a fragment of one that has lost its normal function. The majority of M proteins are IgG (~50%) and IgA (~20%). The proliferation of myeloma

cells causes displacement of the normal bone marrow. In MM, the major clinical findings include anemia, monoclonal immunoglobulin (M protein) in serum, abnormal bone radiographs (bone resorption seen as diffuse osteoporosis and/or characteristic lytic lesions), hypercalcemia, renal insufficiency or failure, and neurological complications. MM accounts for approximately 1% of all malignancies and 10% of all hematologic malignancies with a higher frequency in African Americans where MM accounts for 20% of all hematologic malignancies (2). In the US, approximately 11,000 deaths each year are related to MM, and the estimated number of new cases of MM is rising from 15,270 in 2004 to 16,500 in 2006, a rise of approximately 8% (3). At present, no cure is available, and the mean survival is approximately 3-5 years, with a 10% 10-year survival.

2.2 Current Treatment of Multiple Myeloma

Current treatments include combination chemotherapy, proteasome inhibitors, immunomodulatory drugs (IMiDs) high dose chemotherapy and stem cell support. Allogeneic transplantation is performed only in a minority of younger patients and its role as treatment modality is not determined.

Combination Chemotherapy:

Chemotherapy includes the use of alkylating agents, such as melphalan and cyclophosphamide, vincristine, anthracyclines (e.g. doxorubicin) or glucocorticosteroids or combinations of these. Overall response rates (ORR) are in the range of 20-60%.

Melphalan is an alkylating agent and a derivative of meclorothamine. The main target is doublestranded DNA, and melphalan causes both strand breaks and induces cross-links between the two DNA strands, thus interfering with gene transcription. Melphalan is described to be cell cycle nonspecific, however it is believed that proliferating cells are more susceptible due to less time for DNA repair to occur. Long term side effects include increased risk of developing myelodysplasia, treatment-related acute myeloid leukemia, infections, thrombocytopenia, neutropenia, nausea and alopecia. Furthermore, due to alkylating activity, melphalan should not be administered to patients eligible for transplantation before stem cells are harvested. The **melphalan/prednisone** (MP) regimen was introduced more than 40 years ago, and a response rate of 65% in treatment naïve patients has been reported (4). However, in the vast majority of cases patients responding to the MP treatment only obtain a partial response (PR). In general melphalan combination regimens have only had limited impact on overall survival (OS). The MP regimen is widely used as 1st line treatment for elderly patients. Additions to the MP regimen seem to have a positive effect on complete response (CR) rates and OS (see below under bortezomib, thalidomide and lenalidomide). Such triplet combination might become standard treatment for elderly patients with myeloma within a few years. In summary, MP is approved and until recently applied as 1st line for elderly patients with some response but no effect on OS, but novel combinations, e.g. MP + thalidomide (MPT) seem to offer improved response rates and survival benefit.

Proteasome inhibitors

Bortezomib (Velcade®) is an anti-neoplastic agent which was approved by the FDA in 2003 (3rd line) and 2005 (2nd line) for relapsed/refractory patients with MM. Response rates of around 30% in relapsed patients have been reported with <3% CR (5). However, AEs occurring in 30-70% of patients include anorexia, constipation,

thrombocytopenia, neutropenia, pyrexia, vomiting, and anemia. Of particular importance, treatment-associated peripheral neuropathy is frequently reported. Recently, bortezomib has been tested in 1st line setting as induction therapy with an ORR of 49%, with no CR (n=43, phase II) (6) and in 2nd and 3rd line settings with an ORR of 70% and CR of 3-12% (Phase III studies of n=624, n=104, and n=333) (7;8), (9). Furthermore, clinical trials with bortezomib in combination with other therapies, including dexamethasone, dexamethasone/doxorubicin, revlimid, and melphalan/prednisone have been conducted. Especially, bortezomib in combination with melphalan/prednisone as 1st line has yielded high response rates of 89% including CR of 32% and a 2-year survival of 86% (n=60, phase I/II) (10). However, high frequencies of side-effects were observed, including thrombocytopenia (51% of the patients), neutropenia (43%) and neuropathy (17%). Recently, combination of bortezomib with thalidomide as 1st line therapy has also yielded high response rates (82%) (n=30), however all patients developed neurological AEs (11). Also, bortezomib in combination with dexamethasone, 1st line, is shown to yield high response rates of 90% with CR/near CR of 19% (n=48, phase II) (12). Additionally, a quadruple combination with bortezomib, MP and thalidomide in 2nd/3rd line has shown high response rates (70-80%) with CR in around 30% of the patients (n=30, phase I/II) (13). However, the high frequency of associated SAEs of grade 3 and 4 such as thrombocytopenia (~30%), neutropenia (~40%) and peripheral neuropathy (~5%) should be noted. In summary, bortezomib is currently used as 2nd and 3rd line therapy for relapsed/refractory patients with MM. Future bortezomib combination regimens are likely to include MP or dexamethasone for 1st line therapy.

Carfilzomib (formerly known as PR-171) is a tetrapeptide epoxyketone-based inhibitor of the chymotrypsin-like activity of the 20S proteasome. Carfilzomib, which is structurally and mechanistically different from the dipeptide boronic acid proteasome inhibitor bortezomib, showed less off-target activity when measured against a broad panel of proteases including metallo, aspartyl, and serine proteases compared to bortezomib; the latter showed off-target inhibitory activity in the nanomolar range against several serine proteases (29). In addition, carfilzomib is more selective for the chymotrypsin-like protease activity of the proteasome than bortezomib. This selectivity may be responsible for the reductions in myelosuppression and neuropathy observed in preclinical studies comparing carfilzomib with bortezomib. Carfilzomib is approved (in the US) for the treatment of patients with relapsed MM who have received one to three previous lines of therapy, in combination with lenalidomide and dexamethasone.

Thalidomide and analogues (Immunomodulatory Drugs - IMiDs)

Thalidomide has been used as a single agent in the treatment of relapsed patients with MM. Response rate in monotherapy is approximately 30% with a progression-free survival (PFS) in the range of 5 to 9 months (14), (15). In 2006, thalidomide was approved for 1st line treatment in combination with dexamethasone. This combination results in response rates of around 60%, however only very few CRs (4%) were observed and a high frequency of side effects including deep venous thromboembolism (DVT) and neuropathy was reported (n=103, phase III) (16), (17). In particular, the occurrence of neuropathy increases with duration of therapy, an issue which is important for maintenance therapy (18). Thalidomide has now also

been tested in elderly patients in combination with standard MP-regimen, in particular with improved CRs (MPT, 15% vs. MP, 4%) and a 3-year survival of 80% (n=129 and 126 respectively, phase III) (19).

Lenalidomide (Revlimid®) is approved 1st line treatment in combination with dexamethasone. As monotherapy in refractory patients, a response rate of 37% with 10% CR has been reported (20). Severe side effects include thrombocytopenia and neutropenia. Lenalidomide plus dexamethasone versus dexamethasone alone in relapsed patients show increased overall response (59% vs. 23%) with CR of 8-17% vs. less than 3%, and increased overall survival (n=346 in each arm, two phase III studies) (21), (22). In addition this combination has also been tested as 1st line treatment showing an ORR of 91% including 18% CR and a 2-year overall survival of 91% (n=34, Phase II) (23), (24). Lenalidomide is also tested in a 1st line setting as an add-on to MP (MPR) vs. MP alone with a reported RR of 85% including a CR of 23% (n=34, Phase I/II) (25). Interestingly, peripheral neuropathy does not seem to be an issue with lenalidomide – in contrast to thalidomide.

Pomalidomide (Investigational Product) is approved for the treatment of MM in patients who have received at least two prior therapies (including lenalidomide and velcade) and have demonstrated disease progression after the last treatment. Pomalidomide is a novel immunomodulatory drug, which shares some of the beneficial pharmacologic properties of lenalidomide and thalidomide. It has shown a 10-fold higher potency for T-cell stimulation than lenalidomide (30) and is more potent than both lenalidomide and thalidomide in inducing G1 growth arrest and apoptosis in MM cell lines and in patients MM cells that are resistant to melphalan, doxorubicin and dexamethasone, as well as enhancing the antimyelomatous activity of dexamethasone (31). Moreover, pomalidomide does not inhibit the proliferation of normal B cells but rather protects them from apoptosis, assisting the repopulation of normal blood cells (32).

Transplantation

In younger patients, autologous stem cell transplantation (ASCT) has been performed following induction therapy. This resulted in CR rates in the range of 20-40%, (26) and in prolonged OS, i.e. 21% 7-year survival rate, which could be improved if an additional transplantation was performed, especially in patients obtaining less than a very good partial response to the first transplantation (27). ASCT is now used as front line treatment in younger patients and in patients with high performance score. Each year more than 4,000 patients with MM in the US receive a stem cell transplant, thus only offered to approximately 25% of newly diagnosed patients. Allogeneic stem cell transplantation can lead to prolonged disease-free survival in only a small percentage of treated patients, and is associated with high treatment-related morbidity and mortality (28).

3. STUDY OBJECTIVES

3.1 Primary Objective

[name], 2015

The primary objective of this study is to compare progression-free survival in subjects with RRMM who are receiving Pom/dex vs subjects receiving DEX alone in a randomized multicenter setting.

3.2 Secondary Objective

The secondary objective of this study is to compare the Overall Survival (OS) in subjects with RRMM who are receiving Pom/dex vs subjects receiving DEX alone in a randomized multicenter setting.

3.3 Primary Endpoint

Progression-free survival (PFS)

The primary endpoint of progression-free survival (PFS) defined as the time from randomization to the date of the first documented disease progression using the EBMT criteria or to death due to any cause.

3.4 Secondary Endpoint

Overall Survival (OS)

Survival is defined as the time from randomization to the date of death. Subjects, who do not die, will be censored at the date of last contact ("last known date alive").

4.2 Study schema

4.3 Subject screening

The screening period for a particular subject commences when the subject undergoes the first study-specific screening assessment. Written informed consent must be obtained before any protocol-specific tests or procedures may be conducted. After informed consent is obtained, the following screening assessments will be performed within 21 days before the planned day of randomization unless otherwise stated.

Subjects must have a wash-out period (from any MM treatment) of minimum 21 days prior to randomization.

Subjects who have failed screening because of cytopenias are not allowed to use growth factors to become eligible.

Subject who failed screening will be allowed to be reevaluated for eligibility.

Confirmation of diagnosis, medical history and concomitant medications should also be verified during the screening period.

The start of study treatment dosing is considered as Cycle 1 Day 1. All efficacy assessments should take place on Day 1 of every Cycle (± 2 days) for the PFS phase of the study. LTFU will be performed every 2 months (± 7 days) for the OS part of the study.

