6.5 Dose Delay, Interruption, or Discontinuation

If the dose of one drug in the regimen (ie, pomalidomide or dexamethasone) is delayed, interrupted, or discontinued, the treatment with the other drugs may continue as scheduled.

Subjects experiencing a 28 day delay in all study drugs (pomalidomide and low-dose dexamethasone) due to an adverse event(s) related to study treatment must be discontinued from study drug. Subjects experiencing delays unrelated to study therapy, for example due to radiation therapy may delay study treatment up to 42 days. Delays greater than 28 days must be discussed with the medical monitor.

Patients are considered still on study therapy even if they continue solely on pomalidomide.

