7. EFFICACY ASSESSMENTS

7.1 Efficacy assessment

It must be conducted at the same time points for all subjects during their participation in the study in order to accurately compare PFS between the two treatment arms. These assessments include: myeloma paraprotein protein electrophoresis and immunofixation, serum immunoglobulins, serum free light chain assay, serum hematology (hemoglobin), serum chemistry (corrected serum calcium and creatinine) and bone marrow aspirate. They must be performed at the start of each cycle (28 days). Treatment response must be assessed using results from the central study laboratory.

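### PFS is counted from randomization but assessment visits from first dose, so an unequal start between arms would offset the visit grids and bias the log-rank test

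*Protocol*

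**What the plan says.** - **Start of PFS.** Section 3.3 defines it as the "time from randomization to the date of the first documented disease progression using the EBMT criteria", or to death from any cause. Section 1.7 also counts from randomization.
- **Start of the visit clock.** Section 4.3: "The start of study treatment dosing is considered as Cycle 1 Day 1". The next sentence reads "All efficacy assessments should take place on Day 1 of every Cycle (± 2 days) for the PFS phase of the study". Section 7.1 adds "They must be performed at the start of each cycle (28 days"). Section 7.2 begins response evaluation at the second cycle.
- **Date of progression.** Under section 7.3 it is the date of the earlier of the two qualifying assessments, so it is a visit date.
- **Stated aim.** Section 7.1 says of the efficacy assessment: "It must be conducted at the same time points for all subjects during their participation in the study". The reason it gives is an accurate comparison of PFS between arms.
- **Gap to first dose.** The windows in sections 4.3, 5.2 and 5.3 all look back from randomization. None runs forward to the first dose.
- **Delays on treatment.** Section 6.5 says that subjects delayed for reasons unrelated to study therapy "may delay study treatment up to 42 days". Nothing says whether assessments keep their calendar dates when a cycle is delayed.

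**The concern.** The endpoint and the visits that measure it have different time zeros. A subject dosed g days after randomization has the first response assessment at day g + 28 of PFS time, the next at g + 56, and so on. If g differs systematically between arms, the arms are observed on offset grids. The protocol's own requirement of common time points is then not met, even by a site that follows section 4.3 exactly.

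The visit interval is long against the planned medians of 2 and 3 months (section 9.4), so the test is sensitive to the grid. What is at stake is the type I error of the primary analysis and the estimated hazard ratio. A difference in starting time is conceivable: the trial is open-label, and section 6.2 has pomalidomide supplied by the sponsor while dexamethasone is prescribed from commercial stock. The documents do not say that a difference occurs, or how large it would be.

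**Working it through.** The plan gives no figure for this point, so there is none to reproduce.

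**Inputs from the protocol.** 250 subjects, 1:1; 12-month accrual; control median 2 months; 28-day visits ±2 days; analysis at 125 events; one-sided 0.025. For 3 vs 2 months at 90% power, the Schoenfeld formula gives 4(1.960 + 1.282)² / (ln 0.667)² ≈ 256 events, not 125. That is a separate matter, and this point does not depend on it.

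**Assumptions not in the protocol.** Exponential PFS with the same median in both arms (no true effect); all gaps and slips; in the simulations, 10% of events are deaths dated exactly, and the test is unstratified.

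**Step 1: why average dates barely move.** Progression at true time T is dated at the first visit g + 28k on or after T. Let one arm start 5 days later. Within any 28-day stretch after the first visit, 23 days' worth of events are dated 5 days later and 5 days' worth are dated 23 days earlier: (23 × 5 − 5 × 23)/28 = 0. A small net shift remains from the first interval.

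**Step 2: why the log-rank test still moves.** Take 125 per arm, median 60.9 days (hazard ln 2/60.9 = 0.01138 per day), no jitter, no deaths, DEX gap 0 and Pom/dex gap 5. O − E is for Pom/dex.
- Day 28: 34.11 DEX events; Pom/dex share of the risk set 125/250 = 0.5; O − E = −17.06.
- Day 33: 39.14 Pom/dex events; DEX share 90.9/215.9 = 0.421; O − E = +16.48. Pair: −0.58.
- Day 56: 24.80 DEX events; Pom/dex share 85.9/176.8 = 0.486; O − E = −12.05.
- Day 61: 23.43 Pom/dex events; DEX share 66.1/152.0 = 0.435; O − E = +10.19. Pair: −1.86.

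Each later pair is exp(−28 × 0.01138) = 0.727 times the one before. Total O − E = −0.58 − 1.86/(1 − 0.727) ≈ −7.4. The variance, Σ d·p(1 − p), is 18.07 for the first pair and 11.95 for the second, so the total is 18.07 + 11.95/(1 − 0.727) ≈ 61.9. The implied HR is exp(−7.4/61.9) ≈ 0.89 with no drug effect. At each pair of visits the DEX events are removed just before the Pom/dex events are counted, so the bias comes from ordering.

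**Step 3: simulation, test at 125 events.** A fixed later Pom/dex start is added to a 0–2 day variation in both arms.

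| Pom/dex later by (days) | Rejection favouring Pom/dex | Mean HR | Mean PFS, Pom/dex vs DEX (months) |
|---|---|---|---|
| 0 | 2.5% | 1.00 | 3.33 vs 3.33 |
| 3 | 10.8% | 0.88 | 3.34 vs 3.33 |
| 5 | 13.5% | 0.85 | 3.36 vs 3.32 |
| 7 | 11.7% | 0.87 | 3.37 vs 3.33 |
| 14 | 5.6% | 0.93 | 3.42 vs 3.33 |
| 21 | 2.5% | 0.99 | 3.49 vs 3.33 |
| 28 | 11.1% | 0.87 | 3.56 vs 3.33 |

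Variants (number of events analysed, handling of deaths) put the fixed 3–7 day case between about 8% and 14%.

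**Step 4: other gap patterns.**
- Equal gaps, 0–14 days in both arms: 2.2%, HR 1.00.
- Pom/dex 0–14 days, DEX 0–2: 7.5%, HR 0.91.
- All events observed, DEX 0–7 days: Pom/dex 1–8 gives 3.3%, 0–10 gives 3.9%, 0–14 gives 4.5% and 3–10 gives 6.0%; HR 0.96–0.98.
- DEX later by 5 days: 13.4% favouring DEX, HR 1.17.
- Cycle slip in Pom/dex only: 14 days in 10–30% of cycles gives 3.0–4.2%, HR 0.99–0.97; 7 days in 20% of cycles gives 5.2%, HR 0.95.

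**Step 5: visits counted from randomization.** Type I error is 2.4% in each direction and mean HR 1.00.

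**The case against.** The strongest reply is that the harm depends wholly on a difference between arms that the documents do not show. Dexamethasone is in both regimens, so the prescription step is common to both. Sponsor approval comes before randomization in both arms (section 4.4), and section 6.7 makes sites accountable for both drugs. The largest error rates need nearly every Pom/dex subject to start a fixed few days late. Across 20 sites gaps will vary, and with variation in both arms some results are close to nominal. All of this stands, and it limits the size of the point.

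It can also be said that the 28 days in section 7.1 means a fixed calendar, so that visits would not slip with delayed cycles. That is a fair reading. Slip alone does little in any case, so the point rests on the start gap. A fixed 28-day calendar counted from first dose would still carry that gap.

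A reader might infer that the later arm simply gets later progression dates and longer PFS. The figures do not support this: with a 7-day gap and all events observed, the later arm's mean is about 1 day later and its median about 2 days earlier. Nor is a 28-day delay equivalent to the 1-month difference in medians that the trial targets: a 28-day start gap moves mean PFS by 3.56 − 3.33 = 0.23 month.

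**Conclusion.** The point holds as a weakness of the assessment schedule. The protocol counts PFS from randomization and visits from first dose, leaves the gap between them open, and so does not secure the common time points that section 7.1 asks for.

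With no true effect, the one-sided error (nominal 2.5%) is about 2.5% with equal gaps, 3–8% with unequal gaps that vary within arms, 8–14% with a fixed 3–7 day later Pom/dex start, and 3–5% with cycle slip alone. The bias is not monotone in the gap: in the table it is largest at 5 days, gone at 21 and back at 28. Its direction follows whichever arm starts later, so it cannot be said to favour Pom/dex as such.

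These sizes rest on assumed gaps, exponential PFS and an assumed share of exactly dated deaths. A reader might conclude that the primary analysis is already compromised. The documents do not support that, because they contain no evidence of unequal starts. The change is worth making because it is cheap and closes the route to bias. The design does not fail without it.

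**What to change.** In sections 4.3, 7.1 and 7.2, schedule efficacy assessments every 28 days (±2 days) counted from the date of randomization, in both arms, until progression, regardless of the date of first dose or any cycle delay. Sections 4.3 and 7.1 then agree, and visits and PFS share one time zero. No limit on the interval from randomization to first dose is needed for this purpose, because the gap no longer moves the visits.

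The cost is protocol wording and visit-calendar programming. The small downside is that some assessments will not coincide with a delayed cycle start. The change removes the schedule bias only. It does not address the separate event-count question: at a true HR of 0.667 and 125 events, simulated power with visits counted from randomization is 61%.
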